Appendix 2 Imputation Rules for Missing or Partial Dates for AEs

Date	Situation	Imputation Rule
AE Start Date	Only month and year are known and month is prior to first dose date	Use the first day of the month
	Only month and year are known and month is the same as first dose date	Use the first dose date
	Only month and year are known and month is after first dose date	Use the first day of the month
	Only year is known and year is after first dose date	Use Jan 1 of that year
AE End Date	Only month and year are known and month is prior to last dose date	Use the last day of the month
	Only month and year are known and month is the same as last dose date	Use the last dose date
	Only month and year are known and month is after last dose date	Use the first day of the month
	Only year is known and year is before last dose date	Use Dec 31 of that year
	The estimated stop date is before a complete or imputed AE start date	Use the last day of the month of the AE start date

AE = adverse event

Note: The imputation of end date must be later than start date.

Appendix 3 Imputation Rules for Missing or Partial Dates for Concomitant Medications

Imputation rules for missing or partial dates (D=day, M=month, Y=year, T=time)			
Parameter	Missing	Additional conditions	Imputation Rule
Start date	D only	M and Y same as M and Y of first dose of study drug	Date of first dose of study drug
		M and/or Y not same as M and Y of first dose of study drug	First day of month
	M and D	Y same as Y of first dose of study drug	Date of first dose of study drug
		Y not same as Y of first dose of study drug	Use Jan 01 of Y
	M, D and Y	None--date completely missing	Date of first dose of study drug
	Stop date	M and Y same as M and Y of end of study	Date of end of study
		M and/or Y not same as M and Y of end of study	Last day of month
	M and D	Y same as Y of end of study	Date of last dose of study drug
		Y not same as Y of end of study	Use Dec 31 of Y
	M, D and Y	Medications that are not marked as ongoing - date completely missing	Date of end of study

Appendix 4 SAS Code

SAS code for computing 95% confidence interval for single proportion based on the mid-P method:

```
proc freq data=<dataset> order=freq;
  tables category / binomial (CL=MIDP) alpha=0.05;
  weight Count;
run;
```

SAS code for response-exposure E_{max} model:

```
ods output fitstatistics=<Data with aic>;
ods output parameterestimates=<Data with slope estimates>;
proc nlmixed data=<dataset>;
  by <treatment group>;
  parms Emax=<numeric>
    EC50=<numeric>
    s2=<numeric>;
  mu=(Emax*Cmax) / (EC50+Cmax);
  model <Avg. Slope(0-14)> ~ normal(mu,s2);
run;
```

SAS code for bilinear regression model with κ as one of the parameters:

```
ods output fitstatistics=<Data with aic>;
ods output parameterestimates=<Data with slope estimates>;
ods output additionalestimates=<Data with BA(0-14) estimate>;
run;
proc nlmixed data=<dataset>;
  by <subject ID>;
  parms alpha=4 to 8 by 0.5    betal=-0.3 to 0.3 by 0.05
beta2=-0.3 to 0.3 by 0.05    kappa=2 to 10 by 1    s2=0.05 to 0.3
by 0.05 / best=1;
  bounds alpha >0,    1 < kappa < 14,    s2>0; * Add constraints to
parameters to improve convergence;
  if day <= kappa then mu = alpha + betal*day;
  else if day > kappa then mu = alpha + betal*kappa +
beta2*(day-kappa);
  model logCFU ~ normal(mu,s2);
  estimate 'BACfu(0-14)' (kappa*betal + (t_last-
kappa)*beta2)/t_last; *Estimate BA(0-14);
run;
```

SAS code for bilinear regression model with kappa fixed at 2:

```
ods output fitstatistics=<Data with aic>;
ods output parameterestimates=<Data with slope estimates>;
proc nlmixed data=<dataset>;
  by <subject ID>;
  parms alpha=4 to 8 by 0.5    beta1=-0.3 to 0.3 by 0.05
beta2=-0.3 to 0.3 by 0.05 s2=0.05 to 0.3 by 0.05 / best=1;
  bounds alpha >0,    s2>0; * Add constraints to parameters to
improve convergence;
  if day <= 2 then mu = alpha + beta1*day;
  else if day > 2 then mu = alpha + beta1*2 + beta2*(day-2);
  model logCFU ~ normal(mu,s2);
run;
```

SAS code for simple regression model:

```
ods output fitstatistics=<Data with aic>;
ods output parameterestimates=<Data with slope estimates>;
proc nlmixed data=<dataset>;
  by <subject ID>;
  parms alpha=4 to 8 by 0.5    beta1=-0.3 to 0.3 by 0.05    s2=0.05
to 0.3 by 0.05 / best=1;
  mu = alpha + beta1*day;
  model logCFU ~ normal(mu,s2);
run;
```

SAS code for ANCOVA (lsmeans statement used to estimate 90% CIs, lsmestimate statements used for one-sided 5% p-values, trt = treatment group with HRZE as reference):

```
proc mixed data=<dataset>;
  class <treatment group>(ref=HRZE);
  model <Avg. Slope(0-14)> = <treatment group> + <screening
logCFU> /
* LSmeans used to obtain 90 CIs;
  lsmeans <treatment group> / cl alpha=0.1;
* 6 LSMestimate statements used to obtain 1-sided p-values -
NOTE: HRZE will refer to #6 below if used as reference, the #1-5 will
be as indicated in model;;
  lsmestimate <trt> 'trt #1' 1 0 0 0 0 0 / lower alpha = 0.05;
  lsmestimate <trt> 'trt #2' 0 1 0 0 0 0 / lower alpha = 0.05;
  lsmestimate <trt> 'trt #3' 0 0 1 0 0 0 / lower alpha = 0.05;
  lsmestimate <trt> 'trt #4' 0 0 0 1 0 0 / lower alpha = 0.05;
  lsmestimate <trt> 'trt #5' 0 0 0 0 1 0 / lower alpha = 0.05;
  lsmestimate <trt> 'trt #6' 0 0 0 0 0 1 / lower alpha = 0.05;
run;
```

SAS code for random intercepts and slopes model (day = relative to baseline study day, trt = treatment group with HRZE as reference):

```
proc mixed data=<dataset>;
  class <treatment group>(ref=HRZE) <subject>;
  model logCFU = <day> + <trt> + <day*trt> + <screening logCFU>;
  random int day / subject=<subject> type=un;
* The first 6 estimate statements used to obtain correct 1-sided p-
values - NOTE: HRZE will refer to #6 below if used as reference, the
#1-5 will be as indicated in model;
  estimate "Avg slope Tr 1" day 1 trt*day 1 0 0 0 0 0 / cl lower
alpha =0.05;
  estimate "Avg slope Tr 2" day 1 trt*day 0 1 0 0 0 0 / cl lower alpha
=0.05;
  estimate "Avg slope Tr 3" day 1 trt*day 0 0 1 0 0 0 / cl lower alpha
=0.05;
  estimate "Avg slope Tr 4" day 1 trt*day 0 0 0 1 0 0 / cl lower alpha
=0.05;
  estimate "Avg slope Tr 5" day 1 trt*day 0 0 0 0 1 0 / cl lower alpha
=0.05;
  estimate "Avg slope Tr 6" day 1 trt*day 0 0 0 0 0 1 / cl lower alpha
=0.05;
* The next 6 estimate statements used to obtain correct 90% CIs;
  estimate "Avg slope Tr 1" day 1 trt*day 1 0 0 0 0 0 / cl alpha =0.1;
  estimate "Avg slope Tr 2" day 1 trt*day 0 1 0 0 0 0 / cl alpha =0.1;
  estimate "Avg slope Tr 3" day 1 trt*day 0 0 1 0 0 0 / cl alpha =0.1;
  estimate "Avg slope Tr 4" day 1 trt*day 0 0 0 1 0 0 / cl alpha =0.1;
  estimate "Avg slope Tr 5" day 1 trt*day 0 0 0 0 1 0 / cl alpha =0.1;
  estimate "Avg slope Tr 6" day 1 trt*day 0 0 0 0 0 1 / cl alpha =0.1;
run;
```

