6. HRZE QD

The nomenclatures of study interventions will be used to display in tables, figures, and listings.

All measured variables and derived parameters will be listed individually and, if appropriate, tabulated using descriptive statistics. For categorical variables, summary tables will be provided giving sample size, absolute and relative frequency. For continuous variables, summary tables will be provided giving sample size, arithmetic mean, geometric mean (if appropriate), standard deviation, coefficient of variation (if appropriate), median, minimum and maximum. For variables with non-normal distribution, medians and interquartile range will be calculated, and the appropriate non-parametric tests will be applied. Unless specified otherwise, all confidence intervals will be two-sided 95% confidence intervals. Given the primary endpoint is tested using a one-sided test at 0.05, the corresponding 90% confidence interval will be provided. One-sided p-value will be displayed with 4 decimal places; if the p-value is less than 0.0001, display as “<0.0001”.

Change from baseline or screening for a measured variable at a particular post-baseline time point will be computed as the value at the post-baseline time point minus the baseline or screening value, as appropriate.

Percentages will be displayed with one decimal place and percentages for zero counts will be omitted from the presented results. If the percentage is greater than 0 but rounds to 0.0% (e.g. 0.04%), display as “(<0.1)”.

SAS code of SAS procedures that will be used to perform efficacy and safety analyses is provided in [Appendix 4](#).

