12.1.1 Primary Safety Analysis

AEs with grade 3 intensity or greater are classified as severe AEs. The frequency distribution of participants who experienced 1, 2, or ≥ 3 severe AEs occurring from Day 1 through Day 15 will be summarized by treatment group. The frequency and proportion (expressed in percent) of participants and 95% CI for proportions in each category will be provided. For computing proportions, the denominator is the number of participants in the Safety population for the given treatment group.

Serious AEs will be summarized similarly as described for severe AEs.

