12.2 Eye Symptoms

Analysis of eye symptom-related AEs for all eye symptoms, severe eye symptoms, and serious eye symptoms will be based on new events that occurred after Screening. Severe eye symptoms are events that are assigned with grade 3 intensity or greater.

The frequency distribution of participants who experienced 1, 2, or ≥ 3 eye symptom-related AEs in one or both eyes during Day 1 to Day 15 will be summarized by treatment group for all eye symptoms, severe eye symptoms, and serious eye symptoms. The frequency and proportion (expressed in percent) of participants and 95% CI for proportions will be provided for the summary. For computing proportions, the denominator is the number of participants in the Safety population for the given treatment group.

Additionally, the frequency of symptom-related AEs and frequency and proportion (expressed in percent) of participants with eye symptom-related AEs in one or both eyes will be provided by PT and by treatment group for the following:

- All eye symptoms
- Severe eye symptoms
- Serious eye symptoms
- The frequency and proportion of participants with eye symptom-related AEs in one or both eyes that observed at Days 1, 4, 7, 10, 14, 15, Days 1-15 combined (i.e. any eye symptom-related AE observed on any Days 1-15), 28, 42, and Days 28-42 combined (i.e.

any eye symptom-related AE observed on any Days 28-42) will be provided by treatment group for the following: All eye symptoms

- Severe eye symptoms
- Serious eye symptoms

For the by-time point summary, the denominator for the proportion is the number of participants with eye symptom assessment at the given time point.

Any day that a participant reported an eye symptom-related AE in one or both eyes after screening will be counted toward the number of days of having eye symptoms in the study for that individual. Number of days of having eye symptoms will be summarized by treatment group using descriptive statistics for the following:

- All eye symptoms
- Severe eye symptoms
- Serious eye symptoms

Additionally, categorical number of days of having eye symptoms for participants with these events will be summarized by treatment group as follows:

- 1-3 days
- 4-6 days
- 7-9 days
- 10-12 days
- 13-15 days
- ≥ 16 days

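### The SAP's confidence-interval code for a proportion reports whichever level is most frequent, and only that one, so for rare severe or serious AEs it returns the interval for having no event

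*SAP*

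**What the plan says.** SAP section 9.1 (General Conventions) gives Appendix 4 its standing: "SAS code of SAS procedures that will be used to perform efficacy and safety analyses is provided in" that appendix. The relevant block there is headed "SAS code for computing 95% confidence interval for single proportion based on the mid-P method". It consists of "proc freq data=<dataset> order=freq", then "tables category / binomial (CL=MIDP) alpha=0.05", then a weight statement on a count variable. It has no option naming the event level, no zeros option on the weight, and no statement splitting by treatment group. No other code for a proportion's interval appears in the SAP.

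Two analyses call for such intervals:

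- SAP 12.1.1, the primary safety analysis, summarises "The frequency distribution of participants who experienced 1, 2, or ≥ 3 severe AEs occurring from Day 1 through Day 15" by treatment group and then says "The frequency and proportion (expressed in percent) of participants and 95% CI for proportions in each category will be provided". For the proportions, "the denominator is the number of participants in the Safety population for the given treatment group". Serious AEs are handled in the same way.
- SAP 12.2 uses the same 1, 2, ≥3 layout and the same denominator for eye-symptom AEs: "The frequency and proportion (expressed in percent) of participants and 95% CI for proportions will be provided for the summary".

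Neither section refers back to the Appendix 4 block or says which level is the event.

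**The concern.** The text of SAP 12.1.1 and 12.2 wants the proportion of participants with the event. The code leaves the choice of level to the observed counts. Because the denominator is the whole Safety population of the group, participants without the event must be in the input dataset, and for a rare event they are the commonest level. The interval printed is then for the complement.

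There is also a mismatch in number: one call gives an interval for one level, while SAP 12.1.1 wants one for each category.

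At stake is the interval for the primary safety endpoint. Protocol 9.4.2.1 plans no formal comparison with control, so these intervals are the only statement of uncertainty in that analysis.

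**Working it through.** **Inputs.** N = 15 per group and true AE rates of 5%, 10% and 15% (3% for N = 75) come from SAP 6.2. The two-sided 95% level comes from SAP 9.1. The mid-P method and the code come from Appendix 4. Two default behaviours of PROC FREQ are assumed: without a named level, the binomial request uses the first level of the one-way table; and frequency ordering sorts levels by descending count. SAS itself was not run.

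**The plan's own binomial figures.** The documents state no numerical interval. The chance of at least one AE, 1 − (1 − p)^n, is:

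| n | p | Computed | SAP |
|---|---|---|---|
| 15 | 10% | 0.794 | 80% |
| 15 | 15% | 0.913 | 90% |
| 15 | 5% | 0.537 | 54% |
| 75 | 3% | 0.898 | 90% |

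These reproduce.

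**Mid-P limits.** For x events in n, the lower limit solves P(X > x) + ½P(X = x) = 0.025 and the upper limit solves P(X < x) + ½P(X = x) = 0.025. If (L, U) is the interval for x, the interval for n − x is (1 − U, 1 − L).

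**Two-level variable, n = 15.**

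| Events | Level the code reports | Interval returned | Interval wanted |
|---|---|---|---|
| 0 | No, 15/15 | 0.819 to 1 | 0 to 0.181 |
| 1 | No, 14/15 | 0.713 to 0.997 | 0.003 to 0.287 |
| 2 | No, 13/15 | 0.625 to 0.977 | 0.023 to 0.375 |
| 3 | No, 12/15 | 0.547 to 0.946 | 0.054 to 0.453 |
| 7 | No, 8/15 | 0.287 to 0.768 | 0.232 to 0.713 |
| 8 | Yes, 8/15 | 0.287 to 0.768 | 0.287 to 0.768 |

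The first row can be checked by hand: ½(1 − p)^15 = 0.025 gives p = 1 − 0.05^(1/15) = 0.181, with complement 0.819.

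From 0 to 7 events the no-event level is reported; from 8 upwards, the event level. The chance of 7 or fewer events in 15 is 0.9994 at a true rate of 15%, and higher at 10% and 5%. At the SAP's planning rates, nearly every two-level interval would therefore be for the complement. A group with no events is also likely: 1 − 0.537 = 0.463 at 5% and 1 − 0.794 = 0.206 at 10%.

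**The SAP's categories, with none added to reach the full denominator.** The counts are illustrative.

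| none / 1 / 2 / ≥3 | Level reported | Interval returned |
|---|---|---|
| 11 / 2 / 1 / 1 | none, 11/15 | 0.475 to 0.909 |
| 6 / 4 / 3 / 2 | none, 6/15 | 0.181 to 0.655 |
| 5 / 6 / 2 / 2 | one event, 6/15 | 0.181 to 0.655 |

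The first row should give 0.023 to 0.375 for one event (2/15) and 0.003 to 0.287 for each of the other two categories (1/15 each). None of these is produced. In the second row 9 of 15 (60%) have an event, yet none is still the largest category. The second and third rows return identical limits for different levels, which is what could happen in two arms of the same table if the code is run by arm.

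**The case against.** The best case for the plan is that SAP 12.1.1 and 12.2 state numerator, denominator and interval correctly, and that the Appendix 4 block is a skeleton with placeholder names, not a finished program. A programmer following the text would name the event level. If not, a row showing 13.3% beside limits of 62.5% and 97.7% excludes its own estimate, and checking should catch it. For two levels the right limits are recovered as 1 − U and 1 − L. Counts and percentages are untouched, no success threshold in the documents uses a safety confidence limit, and SAP 9.5 has the IDMC review patient profiles. All of this limits the consequence. It does not make the code right: section 9.1 presents it as what will be used, and the frequency ordering is an explicit choice that produces the fault.

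A reader might also infer more than the documents support:

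- **That the level turns at one half.** This holds only for a Yes/No variable. With none, 1, 2 and ≥3, the largest category is reported and need not be a majority.
- **That arms will be reported in different directions.** This requires a separate run per arm, and the template has no such statement.
- **That 0/15 will appear as 100%.** This depends on a dataset layout the SAP does not give, although the missing zeros option makes it possible.

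**Conclusion.** The code is wrong as written: it selects the level by frequency and gives one interval per call. For a two-level variable with n = 15, the interval is for the complement whenever 7 or fewer have the event (2/15: 0.625 to 0.977 returned, 0.023 to 0.375 wanted). For the categories in SAP 12.1.1, it gives one interval where several are required.

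This rests on the PROC FREQ defaults stated above, which a short test run would confirm, and on participants without an event being in the dataset. If only event rows were kept, the denominator would contradict SAP 12.1.1: counts of 2, 1 and 1 would give 2/4 with limits 0.094 to 0.906.

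The documents do not support a claim that the trial's safety conclusions would change. No information is lost and the two-level error is visible and reversible. It should be corrected because it affects the prespecified interval for a primary endpoint and costs almost nothing to put right.

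**What to change.** In Appendix 4:

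1. Remove the frequency ordering.
2. Create a Yes/No indicator for each reported category (1, 2, ≥3) and for any severe and/or serious AE, by treatment group.
3. Put explicit zero-count rows in the input dataset, so that each group has both a Yes and a No row. The zeros option works only if those rows exist.
4. Use, for each indicator: `by <treatment group>; tables <indicator> / binomial(level='Yes' cl=midp) alpha=0.05; weight Count / zeros;`

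Apply the same to the eye-symptom proportions in SAP 12.2, and add a cross-reference from 12.1.1 and 12.2 to the block.

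The cost is a few lines of code and a small data step. Design, endpoints and data collection do not change.

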a. **Early Withdrawal Visit (EWV) or Unscheduled Visit.** Participants who withdraw before Day 14 will be asked to complete the EWV assessments within 2 Days of withdrawal. Participants who complete the Study Treatment Phase, but do not return for the Day 28 visit will be asked to return for the Day 42 visit. If access to sites is limited due to the local status of the COVID-19 pandemic, the Day 28 and Day 42 visits could potentially be conducted by telephone. Procedures and assessments conducted during an unscheduled visit will be at the discretion of the investigator in consultation with the medical monitor.

2. Introduction

TBA-7371 is a non-covalent inhibitor of mycobacterium tuberculosis (Mtb) deca-prenylphosphoryl- β -D-ribose 2'-epimerase 1 (DprE1), an enzyme involved in mycobacterial cell wall synthesis. TBA-7371 demonstrates potent bactericidal anti-Mtb activity in vitro, with a minimum bactericidal concentration (MBC) similar to its minimum inhibitory concentration (MIC) against replicating Mtb. It has a narrow spectrum, with activity limited to mycobacteria. Like other cell-wall biosynthesis inhibitors, TBA-7371 is not active against low-oxygen induced non-replicating bacteria. TBA-7371 was highly active against a panel of 96 clinical Mtb isolates representative of global phylogeny and geographical origin, and with differing drug-susceptibility profiles, including extensively drug-resistant TB (XDR-TB). The MIC₉₀ of TBA-7371, i.e. the MIC for at least 90% of isolates of this panel, is 0.64 μ g/mL and the MIC range is 0.04-5.12 μ g/mL, where the distribution of MICs is unrelated to the drug-susceptibility or genotype of the strain, suggesting utility globally, and against drug-sensitive and drug-resistant TB. Activity against drug-resistant Mtb isolates is expected for TBA-7371 because its drug target, DprE1, is novel, compared to those of currently used TB drugs. Mtb mutants resistant to TBA-7371 are selected at a frequency of $4-7 \times 10^{-7}$, similar to the reported *in vitro* resistance frequency for clinically relevant anti-TB agents like ethambutol.

No active metabolites of TBA-7371 have been identified thus far.

More information on the PK and pharmacodynamics (PD) of TBA-7371 is provided in the Investigator Brochure.

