10.2 Demographics and Baseline Characteristics

Demographic parameters (age, sex, race, and ethnicity) and other baseline characteristics (body weight, body mass index (BMI), HIV status, CD4+ T-cell count (if HIV-positive), HR, DBP, SBP, current eye symptom, visual acuity impairment in one or both eyes, color vision deficiency in one or both eyes, log CFU on solid culture, TTP in liquid MGIT culture, and log concentration of sputum LAM, drug susceptibility testing for isoniazid and rifampicin, and minimum inhibitory concentrations (MIC) of TBA-7371) will be summarized by treatment group for all participants in the mITT and safety populations.

Continuous variables will be summarized using descriptive statistics (n, mean, standard deviation, and median, minimum, maximum). Categorical variables will be summarized using counts and percentages.

A data listing of demographics and baseline characteristics will be provided.

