regression model for individual participants in each treatment group in order to ensure the Akaike information criteria (AIC) values for the linear and bilinear models are based on the same form of the likelihood function. Suggested starting values for the parameters are $(\alpha, \beta_1) = (6, 0)$ however a grid search approach can be followed to obtain sensible starting values.

If the linear regression model is selected, the average change in $\log_{10}\text{CFU}/\text{mL}$ count per day over 14 days will be estimated by the constant linear regression slope estimate, $\hat{\beta}_{1i}$, i.e.

$$BA_{CFU}(0 - 14)_i = \hat{\beta}_{1i}.$$

Therefore, for each participant, slopes will be estimated using both bilinear and simple linear regression models, and the better fit model based on lower AIC will be selected for that participant and used to estimate $BA_{CFU}(0-14)$. The $\log_{10}\text{CFU}/\text{mL}$ screening measurement used in the model will be the average of the two individual screening measurements. $BA_{CFU}(0-14)$ will be calculated for each participant within a treatment group individually, and then used as the response variable in an ANCOVA model, with a fixed effect for treatment group and screening $\log_{10}\text{CFU}/\text{mL}$ count as a covariate. Treatment group means from the ANCOVA model will be used to quantify the evidence that each of the treatment group mean $BA_{CFU}(0-14)$ is less than 0 (i.e., that the treatment group mean has a negative slope on average). The mITT population will be used for the primary efficacy analysis with analyses using the per-protocol population performed to assess the robustness of results. The SAS PROC MIXED procedure will be used to fit an ANCOVA model.

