13.3 Exposure-Response Analysis

The exposure-response E_{max} model will be used to estimate EC_{90} as follows:

$$BA_{CFU}(0-14) = \frac{E_{max} \cdot C_{max(ss)}}{EC_{50} + C_{max(ss)}} + \varepsilon$$

where:

- $BA_{CFU}(0-14)$ is the average change in log(CFU) counts over each day from screening to day 14.
- E_{max} is the maximal TBA-7371 EBA effect.
- EC_{50} is the expected concentration of TBA-7371 associated with 50% of E_{max} .
- $C_{max(ss)}$ is the steady state C_{max} of TBA-7371 measured at day 14.
- ε is a random error assumed to be normally distributed with mean zero and constant variance σ^2 .

Exposure-response analysis will be performed in the PK population with participants having PK data measured on day 14. The SAS PROC NLMIXED procedure will be used to fit an E_{max} model. Maximum likelihood estimates and corresponding 95% CIs for E_{max} and EC_{50} will be provided. The prediction of EC_{90} to reach 90% of E_{max} is computed as

$$EC_{90} = 9 \cdot EC_{50}$$

95% CI for the estimate of EC90 will be provided. An exposure-response curve of E_{max} model will be produced and vertical reference lines for EC₅₀ and EC₉₀ will be provided for each treatment group as well as overall.

Alternative sigmoid exposure-response model may be explored if deemed appropriate.

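### The overall EC90 fit leaves out screening log CFU, which the primary ANCOVA of the same response adjusts for, across cohorts mostly not randomised against each other

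*SAP*

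**What the plan says.** SAP 13.3 fits an Emax curve to participant-level BA_CFU(0-14), with Day 14 Cmax as the only predictor, and takes EC90 as 9 × EC50. In Appendix 4 the mean line begins "mu=(Emax*Cmax) / (EC50+Cmax". It has no intercept and no covariate. On who is included: "Exposure-response analysis will be performed in the PK population with participants having PK data measured on day 14". That is at most 5 × 15 = 75 TBA-7371 participants. HRZE participants have no TBA-7371 exposure and are not in the fit.

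In SAP 11.1.1 the same per-participant slope is "used as the response variable in an ANCOVA model, with a fixed effect for treatment group and screening" log10 CFU/mL. The random-slopes sensitivity model (SAP 11.1.3.2) also carries that covariate.

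Text and code differ on the level of the fit. The Appendix 4 block runs "by <treatment group>". The text of 13.3 says the curve and its EC50 and EC90 reference lines "will be provided for each treatment group as well as overall". No code for the overall fit is given. The only latitude offered concerns curve shape: "Alternative sigmoid exposure-response model may be explored if deemed appropriate".

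Protocol 6.3.1 states that the design is not randomised across Cohorts I, IV and V. Only II and III are randomised against each other.

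**The concern.** EC90 is the named secondary endpoint for the lowest exposure with maximal EBA, and Protocol 4.2 says the exposure-response relationship will guide regimen selection. In the overall fit, exposure varies largely by cohort, and cohorts follow one another in time. Protocol 1.1.8 expects the study to be prolonged by the pandemic. If later cohorts enrol participants with a higher or lower bacterial load, and load affects the slope, a Cmax-only model reads that difference as an effect of exposure. With no intercept, any such shift has to go into Emax, EC50 or the error. The randomisation to HRZE within cohorts does not help here, because HRZE is outside the fit. The covariate that would absorb much of such a shift is already collected and already used in the primary analysis of the same response, and 13.3 gives no reason for dropping it.

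**Working it through.** **1. The plan's own figure.** The documents state no precision for EC90. Their only efficacy calculation (SAP 6.2) uses N = 15, SD 0.1 and one-sided 5%, and claims 80% (90%) power for a mean reduction of 0.067 (0.079). A one-sample t-test with 14 df has noncentrality 0.067/0.1 × √15 = 2.59 and 0.079/0.1 × √15 = 3.06. Power is 79.4% and 89.7%, so the figure reproduces. It does not bear on EC90, but it supplies the SD range used below: 0.05 to 0.08 observed in the cited bedaquiline study, and 0.1 for planning.

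**2. Where cohort differences can enter.** A fit within one treatment group covers one regimen, so it cannot confuse exposure with differences between dose levels. The overall fit can.

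**3. Bias.** Assumptions not in the documents: Emax −0.15; EC50 = 100 units, the Cmax of a 100 mg dose, so true EC90 = 900; Cmax proportional to the single dose (the three 100 mg regimens share one level) with log SD 0.35; 75 participants; residual SD 0.08; screening load correlated 0.5 with the residual; load in the 400 mg cohort differing by 0.5 SD.

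- Offset in that cohort: 0.08 × 0.5 × 0.5 = 0.02 per day.
- Curve at 200 mg: −0.15 × 200/300 = −0.10. At 400 mg: −0.15 × 400/500 = −0.12.
- The offset therefore equals the whole step from 200 to 400 mg. It can make the curve look flat there, or double the step.

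Median EC90 over 150 simulated trials:

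| Setting | Cmax only | Adjusted |
|---|---|---|
| Correlation 0.5, less killing at 400 mg | 594 | 902 |
| Correlation 0.5, more killing at 400 mg | 1310 | 964 |
| Correlation 0.3, less killing at 400 mg | 766 | 894 |

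The unadjusted errors are 594/900 = 0.66, 1310/900 = 1.46 and 766/900 = 0.85. The adjusted fits also carried an estimated MIC exponent, but MIC had no effect on the simulated response here, so the correction comes from the screening term. Load was centred at its mean in the unshifted cohorts. For scale, the standard error of a difference between 15 and 60 participants is √(1/15 + 1/60) = 0.29 SD. A 0.5-SD difference is thus 1.7 standard errors: sizeable, but not remote.

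**4. Precision.** Different assumptions: Emax 0.12; EC50 again at the 100 mg Cmax; screening SD 1 log10; cohort means varying with SD 0.3; 300 runs. RMSE of log EC90, Cmax only against adjusted for screening load alone:

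| Effect of load, per day per log10 | SD 0.05 | SD 0.08 | SD 0.1 |
|---|---|---|---|
| 0.01 | 0.66 vs 0.66 | 1.36 vs 1.44 | 1.85 vs 1.87 |
| 0.03 | 1.05 vs 0.66 | 1.52 vs 1.36 | 1.82 vs 1.73 |

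With the stronger effect, RMSE falls by 37%, 11% and 5%. With the weaker one it is unchanged or rises, by at most 1.44/1.36 − 1 = 6%. A separate simulation agrees in pattern: 0.61 vs 0.64 and 1.42 vs 1.44 when load is weakly prognostic; 1.01 vs 0.78 (SD 0.05) and 1.58 vs 1.39 (SD 0.1) when strongly.

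**The case against.** The best case against is that no document reports an effect of screening load on the slope, or a difference in load between cohorts. All cohorts share the same entry criteria, including a smear of at least 1+ (Protocol 5.1). The precision gain needs a fairly strong effect and shrinks at the planning SD. Under the assumptions above, EC90 lies at 9 times the 100 mg Cmax while 400 mg reaches about 4 times, so it is an extrapolation whatever the model. All of that stands, and it limits the claim to a possible bias and loss of precision. It gives no reason to omit a covariate that costs so little.

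Four stronger readings are tempting and are not supported:

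- **The printed code mixes exposure with cohort.** It does not, because it fits each treatment group separately. The weakness of those fits is a narrow Cmax range in about 15 participants, where a further parameter would be hard to carry.
- **EC90 is certainly noisier than it need be.** That depends on effects the documents do not give.
- **The model ought to divide Cmax by each participant's MIC.** Baseline MIC is available: "minimum inhibitory concentrations (MIC) of TBA-7371) will be summarized by treatment group for all participants". But the division forces EC50 to be exactly proportional to MIC. In simulation this helped when true (RMSE 0.88 to 0.53). When MIC had no effect, it raised RMSE from 0.64 to about 2.0 and put EC50 about 5-fold too low. The Protocol's Introduction says "the MIC range is 0.04-5.12" µg/mL, a 128-fold span, but that is the minimum to maximum of a 96-isolate panel. The same sentence gives an MIC90 of 0.64, so at least 90% of isolates fall within 0.64/0.04 = 16-fold. MIC is also used through T>MIC in SAP 13.2, although that does not feed EC90.
- **Adjustment would remove all cohort confounding.** It removes only what screening load carries.

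**Conclusion.** The point holds for the overall fit only. That fit omits a baseline covariate the plan already uses for the same response, and it does so where randomisation gives little protection. Under a strong but not extreme assumption (correlation 0.5, a 0.5-SD difference in one cohort), EC90 is about one-third too low or nearly half too high without the covariate, and within about 7% of the truth with it (964/900 = 1.07). If load has little effect, adjustment costs a few per cent in precision. All of these figures rest on simulation assumptions, not on data in the documents. Adjustment will not make EC90 precise: at SD 0.1 the adjusted RMSE of 1.73 on the natural-log scale is still a typical error of about e^1.73 = 5.6-fold. This is a worthwhile refinement of a secondary endpoint, with no bearing on the primary test.

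**What to change.** In SAP 13.3 and Appendix 4:

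1. Add code for the overall fit without the BY statement, so that text and code agree.
2. In that overall fit, add to mu a linear term: a coefficient times (screening log10 CFU/mL minus its mean over the participants fitted). State the centring value, because without an intercept the fit depends on it. EC90 remains 9 × EC50, now read at the mean screening load. Leave the by-group fits as they are.
3. Optionally, as a sensitivity analysis only, let EC50 vary with baseline MIC through an estimated exponent, EC50 × (MIC / median MIC)^θ, in participants with a baseline MIC. State how missing MICs are handled, since MIC is tested only on positive cultures.

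The required part costs one extra parameter and one further model run on data already collected. SAP 9.2 uses the single available sample when one of the two screening samples is missing, so few participants should be lost.
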